9.2.1. Study Population and Cohorts

The study population will consist of patients who tested positive or were diagnosed for COVID-19 (ie, positive PCR or antigen results of direct SARS-CoV-2 viral testing or have confirmed COVID-19 diagnosis codes). All Paxlovid users will be included in the study.

Within the study population, three source cohorts of general population with COVID-19 will be formed (Figure 1):

- 1a: Overall COVID-19 patients.
- 1b: Hospitalized patients (ie, hospitalized within 30 days of index date) for COVID-19
- 1c: Non-hospitalized patients (ie, not hospitalized within 30 days of index date) with COVID-19

Within source cohort of 1a, 1b, and 1c, the following trial similar subcohorts, will be formed:

Patients at high risk of progression to severe illness (Figure 1)

- 2a: Subgroup of the general population cohort 1a who meet relevant inclusion/exclusion criteria of the Paxlovid clinical trial (C4671005).
- 2b: Subgroup of the hospitalized patient cohort 1b who meet relevant inclusion/exclusion criteria of the Paxlovid clinical trial (C4671005).
- 2c: Subgroup of the non-hospitalized patient cohort 1c who meet relevant inclusion/exclusion criteria of the Paxlovid clinical trial (C4671005).

Patients at standard risk of progression to severe illness Figure 1)

- 3a: Subgroup of the general population cohort 1a who meet relevant inclusion/exclusion criteria of the Paxlovid clinical trial (C4671002).
- 3b: Subgroup of the hospitalized patient cohort 1b who meet relevant inclusion/exclusion criteria of the Paxlovid clinical trial (C4671002).

[figure not shown]
 3c: Subgroup of the non-hospitalized patient cohort 1c who meet relevant inclusion/exclusion criteria of the Paxlovid clinical trial (C4671002).

A sub-cohort of patients who were exposed to Paxlovid in real world settings will be created.

If a patient had an exposure to paxlovid without COVID PCR/antigen testing/diagnosis data, this patient can be captured in the Paxlovid cohort.

Additional special populations (eg, immunocompromised patients, pediatric population, severe renal impairment, etc.) may be added as a subset.

A validation substudy will be a subpopulation randomly drawn from within the OPTUM EHR database. Figure 1. Flowchart Outlining the Study Cohort and Subcohorts

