9.2.2.3. Index Date

The index date for the COVID-19 Source and the Trial Similar Subcohort will be defined as the date of first date tested positive or diagnosed for COVID-19 (ie, positive PCR or antigen results of direct SARS-CoV-2 viral testing or have confirmed COVID-19 diagnosis codes) during the study period.

Method to refine index date per research question will be defined in SAP.

The index date for the Paxlovid cohort will be defined as the date of first prescription of Paxlovid during the study period.

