9.2.2.4. Follow-up

The follow-up period starts at index date and participants will be followed until the date of the first occurring of the following events:

- Death;
- At the end of their database disenrollment from the database;
- At the end of study period (Section 9.2.2.1);
- Occurrence of the outcome of interest.

Follow-up time for hospitalized patients will meet the criterion in Section 9.2.1 (ie, hospitalized within 30 days of COVID 19 diagnosis or index date). Details as well as follow-up windows for long COVID will be defined in SAP.

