9.4. Variables

Outcome events will be the pre-specified potential safety concerns, including those that were part of Paxlovid or identified after the EUA post marketing. The list of events of interest is provided below. This list of outcome events was chosen based on clinician's expert opinion, biologic plausibility, and feasibility of identification in EHR or claims data. Other potential safety concerns that arise during the post marketing, clinical trials, or based on emerging literature related to Paxlovid safety will be included in subsequent refreshes of the cohorts, or as rapid queries in response to regulatory authority requests.

Potential Safety Outcomes of Interests*

- 1. Renal impairment.
- Hepatic impairment.
- 3. Other potential safety events of interest (eg, Diarrhea, Dysgeusia, Hypersensitivity reaction/allergic reactions, and other additional potential safety events of interest may be added over time).

* The potential safety outcomes of interests listed above can be further evaluated by the covariates including (demongraphics, drug-drug interactions etc.).

Potential effectiveness of interests*

- Hospitalization;
- All-cause mortality;
- ICU/Mechanical Vitalization;
- In Hospital death.

COVID-19 complications/interventions (within 30 days of COVID 19 diagnosis):

- Pneumonia;
- Kidney failure;
- Thrombotic event;
- Acute respiratory distress syndrome (ARDS);
- HF;
- Sepsis/septic shock;
- Hospitalization;
- All-cause mortality;
- In hospital death;
- Multi-organ dysfunction/failure;
- Mechanical ventilation/ECMO (Extracorporeal membrane oxygenation).
- Vasopressor use

Time to clinical events:

- Time from index date (Section 9.2.2.3) to admission;
- Time from index date (Section 9.2.2.3) to the events above.

^{*}The outcomes may be removed to added depending on the data availability for proper analyses.

COVID-19 long term health effects:

Headache;

The following conditions may be considered for COVID-19 long term effects. This is not an exclusive list. Specific definition and follow up windows of long COVID (eg, greater than 4 weeks, 12 weeks, or 6 months after a COVID diagnosis)⁹⁻¹⁰ will be further defined in SAP.

4 weeks, 12 weeks, or 6 months after a COVID diagnosis) ⁹⁻¹⁰ will be further defined in SAP.
Abdominal pain;
Acute kidney injury;
Alopecia;
Body aches;
• Chest pain;
Cognitive impairment;
• Confusion/delirium;
Nasal congestion;
• Cough;
Anxiety disorders;

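### Cohorts b and c are defined by admission within 30 days of index, but follow-up starts at index: 30-day hospitalization is fixed at 100% or 0%, and pre-admission time in the b cohorts is immortal for death and in-hospital events

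*Protocol*

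**What the plan says.** Protocol section 9.2.1 forms 1b as "Hospitalized patients (ie, hospitalized within 30 days of index date) for COVID-19" and 1c as "Non-hospitalized patients (ie, not hospitalized within 30 days of index date) with COVID-19". The trial-similar cohorts are nested in these; 2b, for example, is the "Subgroup of the hospitalized patient cohort 1b who meet relevant inclusion/exclusion criteria of the Paxlovid clinical trial (C4671005"), and 3b, 2c and 3c follow the same pattern.

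Section 9.2.2.3 sets time zero for all of these cohorts: the index date "will be defined as the date of first date tested positive or diagnosed for COVID-19". Section 9.2.2.4 then says "The follow-up period starts at index date". Section 9.9 repeats this start for the incidence analysis and makes no exception for the b or c cohorts. The one sentence in 9.2.2.4 about hospitalized patients restates the 30-day criterion and gives no other start date.

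Section 9.4 lists hospitalization, all-cause mortality and in-hospital death among the complications counted within 30 days of diagnosis, and adds "Time from index date (Section 9.2.2.3) to admission" as a time-to-event variable. Section 9.9 asks for the cumulative incidence and incidence rate of each endpoint in the source and trial-similar cohorts. Section 8 names hospitalized and trial-similar patients among the populations for which background incidence is wanted.

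**The concern.** Membership of a b or c cohort is settled by what happens up to day 30, but the person-time and the 1-Kaplan-Meier curves begin on day 0. Conditioning on the future in this way has two effects.

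First, an outcome that is also the membership rule stops being an estimate. Second, a patient admitted on day 7 enters the b cohort only by surviving to day 7, so those seven days add person-time in which death, or any event that needs an admission, could not be counted. A patient who dies at home on day 5 goes to the c cohort instead.

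Primary objectives 2 and 3 (time to clinical events and background incidence) are reported in these cohorts, and section 7 says the rates are meant as context for interpreting possible safety events. A background mortality rate in hospitalized patients that is too low would make a rate observed elsewhere look raised.

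**Working it through.** The protocol states no sample size, event rate or admission delay, so there is no figure of its own to reproduce.

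**Step 1: what follows from the definitions alone.** Read the 30-day window as running after index. Section 9.3.2.1 excludes trial-similar patients hospitalized in the 30 days before index, so this reading is firm for 2b/3b. For 1b it is the natural reading, although the wording gives no direction.

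| Quantity, days 0 to 30 | b cohorts | c cohorts |
|---|---|---|
| Hospitalization | 100% | 0% |
| In-hospital death | can occur | 0 |
| Death before any admission | 0 | all such deaths fall here |

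The zeros in the c cohorts hold only to day 30. Hospitalization in the effectiveness list of section 9.4 carries no 30-day limit, so later admissions can still be counted there.

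**Step 2: size of the rate bias (assumed delays).** Let m be the mean number of days from index to admission in a b cohort and W the follow-up window. Ignoring person-time lost to death, the immortal share is m/W, and the rate is understated by the factor W/(W − m).

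| m (assumed) | Share, W = 30 | Factor, W = 30 |
|---|---|---|
| 0 | 0% | 1.00 |
| 2 | 2/30 = 7% | 30/28 = 1.07 |
| 5 | 5/30 = 17% | 30/25 = 1.20 |
| 7 | 7/30 = 23% | 30/23 = 1.30 |
| 10 | 10/30 = 33% | 30/20 = 1.50 |

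With W = 180 days, a 5-day delay gives 5/180 = 2.8% and a factor of 180/175 = 1.03. These factors apply to incidence rates of death and in-hospital events. They do not carry over to the cumulative incidence.

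**Step 3: simulation check.** One million patients per scenario. All inputs are assumptions: 5%, 10% or 20% admitted within 30 days; exponential admission times with parameter 3, 7 or 12 days, truncated at 30; and a 30-day death hazard of 0.002 without admission and 0.10 after admission. The results at 10% admitted were:

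| Parameter (days) | Immortal share of 1b | Deaths per 1000 person-days, from index | From admission | Ratio |
|---|---|---|---|---|
| 3 | 10.4% | 2.99 | 3.34 | 1.12 |
| 7 | 22.7% | 2.57 | 3.32 | 1.29 |
| 12 | 31.9% | 2.25 | 3.31 | 1.47 |

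The 5% and 20% scenarios gave nearly the same shares and rates. In every run 30-day hospitalization was 100% in 1b and 0% in 1c, no 1b patient died before admission, and 1a returned the assumed admission risk.

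**The case against.** The strongest reply is that section 9.2.2.3 leaves refinement of the index date for individual research questions to the SAP, and the amendment table in section 5 says this was added to clarify index date and follow-up. The SAP is not at hand and may already move time zero to admission. That is a fair caution. It does not settle the matter, because 9.2.2.4 and 9.9 state the start of follow-up outright for all cohorts. The only remedy for immortal time that the protocol names, in section 9.9, is confined to the exploratory Paxlovid effectiveness feasibility work.

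Other parts of the reply stand and limit the point:

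- A reader might infer that all six cohorts and all endpoints carry immortal time. They do not. Patients in the c cohorts can die from day 0. Pneumonia, thrombotic events, heart failure, renal or hepatic impairment and diarrhea can be recorded in outpatients, so for them the days before admission are genuinely at risk.
- A reader might take the factors in the working as measured. They are not. Section 9.9 itself flags hospitalization on the date of diagnosis; if that is common, the mean delay approaches 0 and the bias nearly vanishes.
- A reader might conclude that the c cohorts should start at day 30 throughout. That would remove the 30-day complications and the early deaths from them.
- Time from index to admission among admitted patients is a legitimate description, provided it is presented as conditional on admission.
- The 100% and 0% figures are easily recognised as tautologies. The understated mortality and in-hospital rates are not.
- The protocol sets no rule for patients observed for less than 30 days. Placing them in the c cohorts follows from its literal wording, but the SAP may treat them otherwise.

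**Conclusion.** The point holds in limited form, as a should-fix. Followed as written, the protocol fixes 30-day hospitalization at 100% in 1b/2b/3b and 0% in 1c/2c/3c, fixes 30-day in-hospital death at 0 in the c cohorts, and understates rates of death and of admission-dependent events in the b cohorts. The first two results need no numerical assumption, only the after-index reading of the window. If 1b also admits patients hospitalized before index, the 100% is no longer exact there and those patients contribute no immortal time.

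The size of the understatement is an assumption: for 30-day rates, a factor from about 1.0 (mostly same-day admission) to about 1.5 (mean delay of 10 days), and less with longer follow-up.

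The documents do not support the inference that objectives 2 and 3 fail as a whole. Cohorts 1a/2a/3a give valid incidence from index as far as this problem goes, baseline descriptions are untouched, and section 9.7 describes the study as descriptive, with comparative analyses outside its scope.

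**What to change.** Amend sections 9.2.2.3, 9.2.2.4 and 9.9 as follows.

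1. For 1b/2b/3b, start follow-up for mortality and in-hospital endpoints at the later of the index date and the admission date. Taking the later date also keeps time zero from falling before the COVID-19 diagnosis if 1b includes earlier admissions.
2. Report hospitalization incidence only in 1a/2a/3a. Present time from index to admission in the b cohorts only as a description conditional on admission.
3. Label 30-day results in 1c/2c/3c as conditional on no admission by day 30. Use a day-30 landmark only for outcomes after day 30.
4. Flag patients who leave the data alive before day 30 without an admission as unclassified, or show a sensitivity analysis without them. Keep early deaths without admission visible.

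The cost is some extra programming and start dates that differ by endpoint, which the tables must state. No new data are needed.

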9.2.2. Time Periods

9.2.2.1. Study Period

The study will include an overall study period and four sub-periods for each source cohort and subcohort (Figure 2):

Figure 2. Flowchart Outlining the Study Periods

- Study period: COVID-19-era (T+) will include Jan 1, 2020 most recent data available at the time of analytic dataset creation. The study period will be further stratified as follows:
 - Study period i (T1): Active COVID-19-era (Pre-Vaccine Period) will include Jan 1, 2020 – Oct 31, 2020
 - Study period ii (T2): Active COVID-19-era (Vaccine Available Period) will include Dec 13, 2020 – most recent data available at the time of analytic dataset creation.
 - Study period iii (T3): Omicron Period (Approximate time period when Omicron is dominated) will include Dec 20, 2021 (TBD).
 - Study period iv (T4): Paxlovid Period (Paxlovid Available after EUA) will include Dec 22, 2021 (ie, EUA approval) to most recent data available at the time of analytic dataset creation.
 - Note: The period(s) for future variant(s) may be added.

9.2.2.2. Baseline Period

The 365 days before index date (see Section 9.2.2.3) will be the baseline period (Figure 2).

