9.2. Setting

This study will be conducted using Optum's COVID-19 Electronic Health Record Data during the period of January 01, 2020, to June 30, 2024. Details about the database are found in Section 9.6. The COVID-era cohorts will be refreshed annually to include additional individuals, follow-up time, and events. These refreshes and cohorts will accordingly be described in a Statistical Analysis Plan (SAP) or protocol amendment as appropriate.

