9.3.2.1. TSC Standard Risk Cohort and TSC High Risk Cohort

Patients meeting any of the following criteria in the TSC high risk cohort (C4671005) or TSC standard risk cohort (C4671002) will not be included in the study:

1. Females who are pregnant or breastfeeding within 9 months prior to index date.

Any time prior to index date, unless specified otherwise:

- 2. History of hospitalization within 30 days prior to Index date.
- Known medical history of active liver disease (other than nonalcoholic hepatic steatosis), including chronic or active hepatitis B or C infection, primary biliary cirrhosis, or acute liver failure.
- 4. Receiving dialysis or end stage of renal disease.

Additionally, patients meeting any of the following criteria in the TSC standard risk cohort (C4671002) will not be included in the study:

Has at least 1 characteristic or underlying medical condition associated with an increased risk of developing severe illness from COVID-19, including:

- ≥65 years of age at the index date.
- BMI≥30 kg/m².
- "High Risk Cohort Inclusion Criteria 1.c 1.1" (Section 9.3.1.1).

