9.5. Covariates

Covariates will include baseline demographic, clinical characteristics, medications, and health utilization, as well as those needed for the study cohort inclusion and exclusion criteria. These are not intended to be the exclusive lists. Adjustments of the covariates may be made and additional variables may be added in SAP as needed over time. The code lists of conditions and medications (if applicable) will be provided in SAP.

Demographics:

- Age;
- Gender;

- Race;
- Ethnicity;
- Region;
- Insurance.

Clinical Characteristics:

- Asthma;
- Autoimmune diseases.
 - Multiple Sclerosis; Sjogren's syndrome; Guillain-Barre; idiopathic thrombocytopenia purpura; autoimmune thyroiditis; giant cell arteritis; psoriasis; systemic or cutaneous lupus erythematosus; autoimmune arthritis/rheumatoid arthritis, glomerulonephritis.
- BMI.
- Cancer.
- Cerebrovascular disease or stroke (including transient ischemic attack).
- CKD.
- COPD.
- ILD.
- Coronary heart disease.
- Cardiomyopathies.
- Deyo-Charlson Comorbidity Index Score.
- Hepatitis B virus (HBV), HCV, HIV infection.
- Hyperlipidemia.
- Hypertension.
- Liver disease.
- Sickle cell disease.

- Smoking.
- Diabetes mellitus.
- Pregnancy status.
- C-Reactive Protein (CRP; within 10 days prior to the index date).
- Lactate dehydrogenase (LDH; within 10 days prior to the index date).
- Ferritin (within 10 days prior to the index date).
- D-dimer (within 10 days prior to the index date).
- Note: A focus of these lab tests would be for inpatients.

Medications that are contraindicated with Paxlovid (FDA EUA label):

- Alpha1-adrenoreceptor antagonist: alfuzosin;
- Analgesics: pethidine, propoxyphene;
- Antianginal: ranolazine;
- Antiarrhythmic: amiodarone, dronedarone, flecainide, propafenone, quinidine;
- Anti-gout: colchicine;
- Antipsychotics: lurasidone, pimozide, clozapine;
- Ergot derivatives: dihydroergotamine, ergotamine, methylergonovine;
- 3-hydroxy-3-methylglutaryl co-enzyme A (HMG-CoA) reductase inhibitors: lovastatin, simvastatin;
- PDE5 inhibitor: sildenafil (Revatio®) when used for pulmonary arterial hypertension (PAH);
- Sedative/hypnotics: triazolam, oral midazolam;
- Anticancer drugs: apalutamide;
- Anticonvulsant: carbamazepine, phenobarbital, phenytoin;
- Antimycobacterials: rifampin;

• Herbal products: St. John's Wort (hypericum perforatum).

Medications for treatment of COVID-19/Vaccination for COVID-1:911

Anti-SARS-CoV-2 Antibody Products			
Bamlanivimab/Etesevimab			

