Casirivimab/Imdevimab			
Sotrovimab			
Tixagevimab/Cilgavimab			
Bebtelovimab			
Convalescent plasma			
Antiviral therapy			
Remdesivir			
Molnupiravir			
Chloroquine /hydroxychloroquine			
Azithromycin			
Lopinavir/ritonavir			
Ivermectin			
Nitazoxanide			
Ribavirin			
Inteferon-beta			
Immunomodulators			
Systemic Corticosteroids			
Dexamethasone			
Methylprednisolone			
Fluvoxamine			
Interleukin inhibitors			
Tocilizumab			
Sarilumab			
Antithrombotic Therapy			
Heparin			
Covid-19 vaccines			

Health Utilization:

- Emergency room (ER) visit;
- Office visits;
- Telemedicine visits;
- Urgent care visits;
- Number of hospitalizations;

Length of hospital stay.

Paxlovid User Characteristics (in addition to Clinical Characteristics, Medications in "Covariates" in the Section 9.5).

- Demographics.
 - Age. Gender.
 - Race.
 - Ethnicity.
 - Region.
 - Insurance.
 - Comorbidities.
 - Renal impairment.
 - Hepatic impairment.
 - Top 50 Comorbidities in the database.
 - Medications.
 - Top 50 prescriptions in the database.
 - Paxlovid use.
 - Days since index date (Paxlovid prescribed date).
 - Provider.
 - Health Utilization:
 - ER visit.
 - Office visits.
 - Telemedicine visits.
 - Urgent care visits

- Number of hospitalizations
- Length of hospital stay

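### The single 365-day baseline carries no exception for COVID-19 vaccination, so by default a patient whose last recorded dose is more than a year before index is not captured as vaccinated

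*Protocol*

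**What the plan says.** Section 9.2.2.2 defines baseline once, for all cohorts: "The 365 days before index date (see Section 9.2.2.3) will be the baseline period (Figure 2". Section 9.5 then describes the covariates as baseline variables: "Covariates will include baseline demographic, clinical characteristics, medications, and health utilization". The table of COVID-19 treatments and vaccination in that section ends with the row "Covid-19 vaccines", with no look-back beside it.

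Other items do carry their own windows:
- In section 9.5 the inflammatory and coagulation markers have a short one, for example "C-Reactive Protein (CRP; within 10 days prior to the index date".
- In section 9.3.1.1, immune-weakening treatment is read over 90 days.
- In section 9.3.2.1, several trial-similar exclusions are read over the whole history: "Any time prior to index date, unless specified otherwise".

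The relevant dates are also in the protocol. Section 9.2.2.1 gives "Active COVID-19-era (Vaccine Available Period) will include Dec 13, 2020" and "Paxlovid Period (Paxlovid Available after EUA) will include Dec 22, 2021 (ie, EUA approval". Section 9.2 gives the data window: "during the period of January 01, 2020, to June 30, 2024". Section 9.6 states that the records reach back to 2007. Section 9.5 allows covariates to be adjusted in the SAP, which was not available for this review.

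**The concern.** A year of look-back suits most of the section 9.5 list, because chronic conditions and regular medicines tend to reappear in the record. A vaccine dose is a one-time entry. Once it is older than the window, nothing later in the record need show it.

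Three uses are exposed:
- **Vaccinated subset.** Sections 9.2.1 and 9.9 name vaccinated patients as a possible subset. With the short window it would omit those vaccinated longest ago and lean towards recent vaccinees, increasingly so at each annual refresh. Background incidence in that subset would then describe a narrower group than its label suggests.
- **Descriptive covariate.** The recorded proportion vaccinated would be too low at later index dates, and the shortfall would vary with calendar time.
- **Modelling.** If vaccination enters the prediction models or the propensity score of section 9.9, it would enter with error that depends on index date.

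**Working it through.** **Inputs.** Baseline look-back: 365 days (9.2.2.2). Vaccine availability starts 13 December 2020 (9.2.2.1). The Paxlovid period starts 22 December 2021 (9.2.2.1). The data window ends 30 June 2024 (9.2). The protocol gives no figure of its own on this point to reproduce.

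**Formula.** For an index date d, let E(d) be the days from 13 December 2020 to d. The window opens at d − 365, so the vaccine-available days out of reach are U(d) = max(0, E(d) − 365), and their share is U(d)/E(d).

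**First affected date.** E = 365 on 13 December 2021, so U = 0. On 14 December 2021, E = 366 and U = 1. The Paxlovid period opens at E = 374, so every index date in it has U of at least 374 − 365 = 9.

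| Index date | E(d) | U(d) = E − 365 | Share |
|---|---|---|---|
| 22 Dec 2021 | 374 | 9 | 2.4% |
| 31 Mar 2022 | 473 | 108 | 22.8% |
| 30 Jun 2022 | 564 | 199 | 35.3% |
| 23 Aug 2022 (protocol date) | 618 | 253 | 40.9% |
| 31 Dec 2022 | 748 | 383 | 51.2% |
| 30 Jun 2023 | 929 | 564 | 60.7% |
| 30 Jun 2024 | 1295 | 930 | 71.8% |

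**What this means for one patient.** At an index date of 30 June 2022 the window opens on 30 June 2021. A patient whose last dose was in spring 2021 has no dose in the window. A patient with the same early doses and a further dose after 30 June 2021 is still seen as vaccinated, although the earlier doses are lost from the count. The patients missed are therefore those whose *last* recorded dose precedes the window, not all who were first vaccinated before it.

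**What cannot be computed.** The document gives no vaccination counts or dose dates, so the shares above cannot be turned into shares of patients.

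**After the change.** With ascertainment from 13 December 2020 or earlier, U(d) = 0 for every index date. The look-back needed is 374 days at the start of the Paxlovid period and 1295 days at 30 June 2024.

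**The case against.** The strongest reply is that the protocol never says vaccination is read only from these 365 days. The row sits in a table made up mainly of COVID-19 treatments, most of which would be given on or after a diagnosis-based index date, so the baseline window cannot sensibly govern every row. Other sections look further back than a year, and section 9.5 leaves covariate adjustments to the SAP, where a look-back for a single covariate would often be set.

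Much of this stands. The 365-day reading is the default, not a quoted rule for vaccines, and the SAP could cure it. But the protocol is not silent here: it states a default window, names exceptions where it wants them, and makes none for vaccination, which for this purpose is a state before index. That default fails on the protocol's own dates.

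A reader might go further in three ways that the document does not support:
- **That such patients are recorded as unvaccinated.** No coding rule says so, and no unvaccinated cohort is defined. The named subset is patients who received vaccines; a short look-back removes people from it but does not add unvaccinated people to it.
- **That up to 72% of vaccinated patients are misclassified.** The percentages are calendar time, and a later dose inside the window still captures the patient.
- **That the Paxlovid comparison is biased by a known amount.** The effectiveness work is an exploratory feasibility objective, section 9.9 does not list the propensity-score variables, and no comparison within an unvaccinated stratum is planned. Any bias figure would need assumed vaccine coverage, vaccine effect and waning.

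**Conclusion.** The point holds as a defect in a stated default. Followed as written, sections 9.2.2.2 and 9.5 together do not capture as vaccinated anyone whose last recorded dose is more than 365 days before index. Some vaccine-available time is out of reach for every index date in the Paxlovid period, but the scale changes greatly: 9 of 374 days at the start, which is negligible, 199 of 564 by mid-2022, and 930 of 1295 at the end of the data window.

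The practical effect is an incomplete vaccinated subset and a weaker descriptive covariate. It extends to prediction and propensity-score work only if vaccination is used there. The conclusion assumes that the general baseline applies to the vaccine row and that the SAP sets no longer look-back. How many patients are affected depends on dose dates that the document does not give.

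**What to change.** In section 9.5, state that COVID-19 vaccination is exempt from the 365-day baseline and is ascertained from all available records before index, starting on 13 December 2020 or at the earliest record. Derive number of doses and time since last dose, and use vaccination in that form wherever it enters: baseline tables, the vaccinated subset and, if it is included, the prediction models and the propensity score.

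The cost is one line of text and a longer query on data already held. The one small drawback is that the length of look-back then varies with index date; reporting time since last dose makes that visible.

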9.9. Data Analysis

Baseline characteristics will be summarized for Source Cohort, Trial Similar Subcohorts, and Paxlovid cohort. Means with standard deviations, medians with interquartile will be provided for continuous variables. Numbers and percentages will be provided for dichotomous variables or categorical variables.

For dichotomous endpoints such as COVID-19 complications and outcomes, the crude cumulative incidence and incidence rate of each endpoint will be estimated for the Source Cohort and the Trial Similar Subcohorts. For incidence calculation, only the first of each event occurring in the risk window will be included in the numerator. How to handle prevalence cases prior to the index date for incidence calculation will be further described in SAP depending on the nature of outcomes (eg, acute vs. chronic evets). Cumulative incidence and its 95% confidence interval (CI) will be estimated and illustrated using 1-Kaplan-Meier curves. Incidence rate will be calculated as the number of patients who experience the event divided by the total person time at risk, along with the 95% CI. The follow-up will start on the index date and will end on the first occurrence of an endpoint, disenrollment, study end date, or death, whichever comes first. Different endpoints will not censor each other's follow-up. Subpopulation analyses, as needed, will be detailed in SAP that may include those immunocompromised patients, pediatric population, severe renal patients, Paxlovid users with contraindication medications, patients with multiple infections of COVID 19, or patients received COVID 19 vaccines etc.

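### Baseline for Paxlovid users runs up to the prescription, so care for the infection being treated can count as baseline in users but never in the source and trial-similar cohorts

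*Protocol*

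**What the plan says.** Section 9.2.2.2 of the protocol defines baseline once, for all cohorts: "The 365 days before index date (see Section 9.2.2.3) will be the baseline period (Figure 2").

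Section 9.2.2.3 then defines the index date in two ways. For the source and trial-similar cohorts it "will be defined as the date of first date tested positive or diagnosed for COVID-19". For treated patients, "The index date for the Paxlovid cohort will be defined as the date of first prescription of Paxlovid during the study period". Between the two definitions stands a deferral: "Method to refine index date per research question will be defined in SAP".

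Section 9.5 states that "Covariates will include baseline demographic, clinical characteristics, medications, and health utilization". The utilization items are ER, office, telemedicine and urgent-care visits, hospitalizations and length of stay. Biomarkers have a shorter window, for example "C-Reactive Protein (CRP; within 10 days prior to the index date"). Paxlovid users also get renal and hepatic impairment, "Top 50 Comorbidities in the database" and a matching list of 50 prescriptions.

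Section 9.9 says: "Baseline characteristics will be summarized for Source Cohort, Trial Similar Subcohorts, and Paxlovid cohort". No section takes the current infection out of the users' baseline.

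**The concern.** A baseline table should describe the patient before the illness under study. In the source and trial-similar cohorts it does, because the window closes before the first COVID-19 record. In a Paxlovid user whose infection was recorded on an earlier day than the prescription, the window stays open through the diagnosis and whatever care followed it. The encounter at which the infection was found is then counted as prior use of care, and its codes and prescriptions as prior history.

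The affected tables serve primary objectives. Objective 1 covers baseline utilization and medical history, and Objective 5 covers comorbidity and utilization in treated patients. A reader who compares the user table with a source table would take part of the difference for a feature of the people treated, when it comes from where the window ends. Under section 9.3.1.2 users are in general patients who met the source criteria, so one patient can appear in both tables with two different baselines.

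**Working it through.** The protocol gives no sample size, power or event figure on this point, so there is none to reproduce. The check is a count of days, followed by an illustration of size.

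**Step 1: day count.** Inputs are the 365-day rule (9.2.2.2) and the two index dates (9.2.2.3). Let D be the day of the first COVID-19 record of the infection, P the day of the prescription, and g = P − D. I read the rule as excluding the index day itself.

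- Source or trial-similar baseline: D − 365 to D − 1. Days on or after D: 0 for every g.
- Paxlovid baseline: P − 365 to P − 1. Days on or after D: g.

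| Gap g (days) | 0 | 1 | 2 | 3 | 5 | 7 |
|---|---|---|---|---|---|---|
| Users: baseline days on or after diagnosis | 0 | 1 | 2 | 3 | 5 | 7 |
| Source: baseline days on or after diagnosis | 0 | 0 | 0 | 0 | 0 | 0 |

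Once g is at least 1, the diagnosis day itself is in the user's baseline.

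**Step 2: does the protocol expect g > 0?** Yes. Section 9.9 plans the prescription time distribution method for immortal time, which presupposes that some prescriptions follow the diagnosis. The share of such users is not given.

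**Step 3: which items move?**

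- Exposed: visit and hospitalization counts, medications, conditions first coded during the infection (renal or hepatic impairment, for example), the users' Top 50 lists, and the 10-day biomarkers, which can be post-diagnosis in users only.
- Hardly exposed: the shared clinical list in 9.5, which is mostly chronic disease such as asthma, cancer, CKD and COPD.
- Not differential: symptom visits before the first positive test or diagnosis, which fall in baseline under either index.

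**Step 4: illustrative size.** The inputs are assumptions, not figures from the documents: a share q of users with g of at least 1, one infection-related visit for each of them, and a true mean of m visits a year. The relative rise in the user mean is q × 1 / m.

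- q = 0.25, m = 8: 0.25 / 8 = 3.1%
- q = 0.60, m = 4: 0.60 / 4 = 15%
- Wider inputs: q = 0.10, m = 8 gives 1.2%; q = 0.75, m = 2 gives 37.5%

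The window keeps its length, so g days drop off its far end. At g = 5 and m = 8 that removes 5 × 8 / 365 = 0.11 visit of ordinary care, well below the one visit added.

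**Step 5: after the change.** If the user window ends the day before the earlier of D and P, the number of baseline days on or after D is 0, as in the source cohorts. Users with no COVID-19 record stay anchored at P.

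**The case against.** The strongest reply is that baseline hangs on the index date and the protocol leaves refinement of the index date to the SAP, which is not at hand. Section 9.5 also lets the SAP adjust covariates, and Figures 2 and 3, which may carry window detail, are not shown. This lowers the weight of the point but does not remove it. The deferral names no rule and concerns the index date, while 9.2.2.2 fixes the baseline rule without deferral.

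A second reply is that closing baseline at treatment start is ordinary for a drug-user cohort. That is right for the user table read alone. The difficulty comes when the same labels are reported for cohorts anchored at diagnosis.

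Three stronger readings are tempting, and the documents do not support them.

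- *Users are made to look sicker across the board.* The shared clinical list is mostly chronic disease, which a diagnosing visit does not create. The Top 50 lists are specified only for users, so they can absorb the treated infection but have no source counterpart to differ from.
- *The protocol plans a user-versus-source contrast.* Section 9.9 says only that baseline is summarized for each cohort, and 9.7 calls the study descriptive and puts post-hoc comparative analyses outside its scope. The comparison is one a reader will make, not one the plan tests.
- *The propensity score is biased.* That analysis is an exploratory feasibility objective and is paired with the prescription time distribution method. Covariates up to the treatment decision are a defensible choice for confounding control.

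The size is also open to challenge. A positive test alone can set the diagnosis date, so not every early-diagnosed user adds a separately recorded visit.

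**Conclusion.** The point holds for the descriptive baseline tables. As written, users recorded with COVID-19 at least one day before the prescription have part of the treated episode in baseline, and source and trial-similar patients do not. Visit and hospitalization counts, medications, newly coded conditions and the 10-day biomarkers are therefore not like-for-like across the cohorts in 9.9. For visit counts the effect is upward in users.

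The size cannot be derived from the documents. A few percent to about 15% of mean visit counts follows from the assumed gap share of 25% to 60%, one extra visit per affected user and 4 to 8 true visits a year; the wider inputs above give 1.2% to 37.5%. Users prescribed on the day of their first COVID-19 record contribute nothing to it. It is worth correcting because primary objectives depend on these tables and the correction is cheap, but it does not invalidate the cohort.

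**What to change.** In 9.2.2.2, for the descriptive baseline tables only, end the Paxlovid cohort's window for utilization, comorbidity and prior medication on the day before the earlier of two dates: the first COVID-19 record of the treated episode, and the prescription. Then:

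- Let the SAP set the window that links a COVID-19 record to the treated episode. This is needed because a user may have an earlier infection, and 9.4 already leaves re-infection and rebound windows to the SAP.
- Keep the prescription as anchor for users with no COVID-19 record, whom 9.3.1.2 admits, and report how many there are.
- Report care between diagnosis and prescription as a separate item, and show for the 10-day biomarkers whether the value precedes or follows the first COVID-19 record.

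The index date for follow-up and the covariate window for the exploratory propensity score need not change.

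The cost is a short addition to 9.2.2.2, one derived date from data already held, and the linking rule in the SAP. The remaining drawback is that users without a COVID-19 record keep a different anchor, which the reported count makes visible.
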